A major objective during the first funding period was to test the hypothesis that an assessment of hippocampal structure could be used to predict the outcome of donepezil treatment in DAT patients. As proposed in our original application, estimates of cognitive decline over time were generated using CDR sum of-boxes scores, ADAS-Cog total scores, MMSE total scores and Neuropsychiatric Inventory (NPI) total scores (see Research Design and Methods section below for more description of these measures). Fifty-one subjects with DAT were included in this analysis and, to date, data were available for a minimum of 48 weeks in 38 subjects (this trial will be completed in the final year of the present funding period). In almost all cases, the subjects had been treated with donepezil, 10 mg/day, for the period of study – in rare subjects that could not tolerate this dose of donepezil, 5 mg/day, was used. In addition, we included data from 65 non-demented subjects (CDR 0) in the analysis, so that we could evaluate variation in hippocampal shape related to drug response in the context of normative structure. To estimate the rate of annual change in the selected clinical measures, a slope value was calculated for each subject using a growth curve model (Laird and Ware, 1982). The mean (SD) annual rate of change for the sum-of-boxes scores was 0.13 (± 0.11 , range -0.06 to +0.41) per year. Other mean (SD) annual rates of change were as follows: ADAS-Cog total score - 0.15 (± 0.29 , range -0.29 to +1.32); MMSE total score - -0.084 (± 0.17 , range - -0.61 to +0.16); the NPI total score - +0.027 (± 0.06 , range -0.03 to +0.37). Thus, in general, mild deterioration was observed in the DAT subjects

treated with donepezil (i.e., slopes for sum-of-boxes scores, ADAS-Cog and NPI scores were positive, while MMSE slopes were negative).

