Prior to initiation of treatment, all subjects will undergo a comprehensive diagnostic evaluation using NINCDS-ADRDA criteria (McKhann, et al, 1984), as well as the CDR ([name], 1993), the Alzheimer Disease Assessment Scale (ADAS; Rosen, et al, 1984), which includes a concise battery of cognitive tests (i.e., the ADAS-Cog), the Mini-Mental State Examination (MMSE; Folstein, et al, 1975), and the Neuropsychiatric Inventory (NPI), to assess the severity of dementia and behavioral symptoms related to dementia. Emergent

side-effects of donepezil and memantine treatment will be recorded using an instrument standard to clinical trials (Treatment Emergent Side-effect Scale [TESS]).

Drug treatment will begin with 5 mg/day of donepezil for six weeks. After six weeks of such treatment, the subjects' symptoms will be re-evaluated and any side-effects of treatment assessed and recorded. If no serious side-effects of donepezil are encountered, the dose of donepezil will be increased to 10 mg/day. For subjects prescribed the combination of donepezil and memantine, memantine (20 mg/day) will be added to the drug treatment regimen after the dose of donepezil has been established (i.e., at six weeks). Again, memantine will be initially started at 10 mg/day and increased to its full dose only if no serious side-effects are encountered. Subsequent evaluations will then be performed every 12 weeks for two years. All evaluations after 6 weeks will include the complete set of clinical and cognitive (i.e., ADAS-Cog) assessments, and a full diagnostic evaluation will be repeated annually (see Flowchart below). MR scans will be collected at baseline and after two years of treatment for all subjects who complete the entire period of treatment. For any subject that discontinues their participation in the study prematurely, the second MR scan will be collected at that time.

Clinical Trial Flowchart

Baseline	Six Weeks	12 Weeks	Every 12 Weeks For Two Years
Donepezil →→ → → → (5 mg/d)	Donepezil → (5 to 10 mg/d)		
	Memantine → (10 to 20 mg/d)		
Diagnosis			Repeat Diagnosis at 1 and 2 Yrs
CDR ADAS-Cog MMSE	CDR ADAS-Cog MMSE	CDR ADAS-Cog MMSE	CDR ADAS-Cog MMSE
NPI	NPI TESS	NPI TESS	NPI TESS
MRI			Repeat MRI at 2 Yrs

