Variables to assess changes in structural volume, thickness, and shape (for the hippocampus) will be generated as described above. Bivariate correlations between changes in clinical and neuroanatomical variables will be estimated using non-parametric statistics (Spearman's rho). To assess whether observed bivariate relationships are independent of each other, a stepwise multiple regression model will be developed including all independent neuroanatomical variables and slope values for the CDR sum-of-boxes scores as the dependent variable.

To test **hypothesis 2** (*The rate of decreasing hippocampal and cortical volumes, thinning of the cingulate and parahippocampal cortices, and changing hippocampal shape will be equal in DAT subjects that are untreated and in DAT subjects that are treated with donepezil alone, but greater than the rate of volume loss, thinning and hippocampal shape change in DAT subjects that are treated with the combination of donepezil and*

memantine.), rates of change for the various neuroanatomical variables will be compared in DAT subjects that are untreated, that are treated with donepezil alone, that are treated with the combination of donepezil and memantine, and in nondemented comparison subjects. These analyses will be performed using simple difference scores (follow-up minus baseline) for volume and thickness variables. To compare rates of change in hippocampal shape across groups, a MANOVA using eigenvectors derived from the time 1-to-time 2 transformation covariance will be performed (see above). The distributional characteristics of each of these variables will be examined prior to hypothesis testing. Finally, non-parametric (Wilcoxon rank sum tests) statistics will be used to compare the groups.

i. Sample Size and Power Considerations

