The risks of donepezil therapy include increased bowel movements, diarrhea, nausea, vomiting, dyspepsia, diminished appetite, and weight loss in approximately 10% of subjects. Less commonly, slight decreases in heart rate, insomnia, and psychomotor agitation have occurred. These side-effects can generally be managed by reducing the dose of donepezil from 10 to 5 mg/day. The side effects of memantine include diarrhea, insomnia, dizziness, headache, and rarely hallucinations. Also, as with any drug, idiosyncratic hypersensitivity reactions can rarely occur. Again, subjects will be warned about these risks, and excluded when they have a history of serious or unstable medical disorders.

5. To minimize these risks, clinical interviews and scanning sessions will be interrupted or discontinued if necessary. Subjects and their caregivers will also be carefully interviewed to exclude the possibility of including anyone with metal embedded in their body. Finally, all drug treatment will be performed in the context of an expert clinic. The DAT subjects will be closely monitored for any drug side-effects, and in subjects who experience such side-effects, the protocol will be discontinued. Personnel trained by the ADRC at Washington University in interviewing and testing DAT subjects will conduct all research-related procedures.

6. The risks of this project are relatively small, and not appreciably greater than the risks of ordinary inpatient assessment and non-invasive radiologic procedures. The drug treatment will be administered to these subjects in the context of ordinary clinical care in the MDC. If successful, knowledge may be gained about neuromorphometric predictors of treatment response in patients with DAT, and perhaps about the pathophysiology of AD in general. In consideration of the small risks and substantial scientific benefit of this work, we consider that risk/benefit ratio to be favorable.

7. All key personnel involved in the design or conduct of the research involving the human subjects will receive the required education on the protection of human research participants prior to funding of this project.

DATA MANAGEMENT

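### Item 5 of Human Subjects, read literally, ends the protocol for any side-effect; this contradicts the dosing rules and adds early exits to a scan comparison that ignores interval

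*Combined protocol and SAP*

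**What the plan says.** Human Subjects, item 5, lists measures to reduce risk. It states: "The DAT subjects will be closely monitored for any drug side-effects", and continues that "in subjects who experience such side-effects, the protocol will be discontinued". The only thing that 'such' can refer to is any drug side-effect. The sentence does not say whether the protocol means drug treatment, study participation or both.

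Other parts of the document treat side-effects differently:

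- Study Design, section a (Overall Design and Source of Subjects), donepezil: "If no serious side-effects of donepezil are encountered, the dose of donepezil will be increased to 10 mg/day".
- The same section, memantine: "memantine will be initially started at 10 mg/day and increased to its full dose only if no serious side-effects are encountered".
- The flowchart in that section schedules the side-effect scale (TESS) at six weeks, at 12 weeks and every 12 weeks for two years.
- Human Subjects, item 4, after listing donepezil's side-effects: "These side-effects can generally be managed by reducing the dose of donepezil from 10 to 5 mg/day". No equivalent is given for memantine.
- Preliminary Studies, on the earlier donepezil cohort: "in rare subjects that could not tolerate this dose of donepezil, 5 mg/day, was used".

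Two further statements decide what an early exit does to the data. Section a says: "For any subject that discontinues their participation in the study prematurely, the second MR scan will be collected at that time". Section h (Data Analysis), for Hypothesis 2, says: "These analyses will be performed using simple difference scores (follow-up minus baseline) for volume and thickness variables". Section h does not mention scan interval.

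**The concern.** A subject with mild nausea at six weeks is titrated up under section a and taken off the protocol under item 5. A clinician cannot follow both. Taken at its word, item 5 would remove subjects whom the dosing procedure means to keep. These would come from the 50 newly recruited combination-treated subjects (Group 3), since they are the ones treated prospectively.

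Two things are at stake. The first is retention: those who remain are fewer and are selected on tolerability. The second is scan timing. If item 5 ends participation, section a moves the second MRI to the exit date, and a shorter interval shows less atrophy for the same underlying rate. Hypothesis 2 concerns rates, but the planned variable is a raw difference. The timing problem arises from any early exit, including deterioration and refusal. Item 5 is only one added source of it.

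**Working it through.** **Step 1. The rules side by side.**

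| Place | Trigger | Consequence |
|---|---|---|
| Human Subjects, item 5 | any drug side-effect | protocol discontinued |
| Section a, donepezil | serious side-effect | no increase to 10 mg/day |
| Section a, memantine | serious side-effect | no increase to full dose |
| Section a, flowchart | none | TESS recorded for two years |
| Human Subjects, item 4 | donepezil side-effect | dose reduction generally suffices |

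For a non-serious side-effect, item 5 and section a give opposite outcomes for both drugs. Item 4 is descriptive and covers donepezil only, so it supports the conflict but does not establish it. The statement in Preliminary Studies reports past practice and is not a rule for this study. No other text limits item 5 to serious or intolerable effects.

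**Step 2. The plan's own figures (section i, Sample Size and Power Considerations).** Of 50 enrolled, 20% attrition leaves 50 × 0.80 = 40. That 20% already includes side-effect withdrawals. For r = .44, n = 40 and two-sided .05, the Fisher z approximation gives power Φ(atanh(.44) × √37 − 1.96) = Φ(2.872 − 1.960) = 0.82, against the stated .80. The plan's figures reproduce.

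**Step 3. Cost in subjects (illustration).** The correlation detectable with 80% power is tanh(2.802/√(n − 3)).

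- n = 40: tanh(2.802/√37) = 0.431.
- n = 35 (five further removals, assumed): tanh(2.802/√32) = 0.458.

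With n held at 35, power for r = .44 is 0.76. Section i allows a slope for anyone with at least five assessments (one year), so only exits before that point are necessarily lost to Hypothesis 1.

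**Step 4. Effect of early scans on the group mean (illustration).** In the untreated CDR 0.5 cohort described in Preliminary Studies, hippocampal loss was 164 mm³ left and 236 mm³ right over a mean of 2.0 years:

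- left: 164/2.0 = 82 mm³/year
- right: 236/2.0 = 118 mm³/year

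Assume linear loss at that rate. A scan at t years instead of 2 shows (2 − t) × rate less loss. If a share s of the analysed group has such scans, the group mean shifts by s × (2 − t) × rate.

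| Exit time t (assumed) | Less loss per early scan, left / right (mm³) | Mean shift, s = 10% (mm³) | Mean shift, s = 2% (mm³) |
|---|---|---|---|
| 1 year | 82 / 118 | 8.2 / 11.8 | 1.6 / 2.4 |
| 0.25 year | 143.5 / 206.5 | 14.4 / 20.7 | 2.9 / 4.1 |

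If only two-year completers are analysed, the shift is 0. If differences are divided by scan interval, the shift under linear loss is also 0. All of these values are below the 50 mm³ that section i treats as detectable. The planned Wilcoxon test works on ranks, so a shift in the mean does not convert directly into an effect on that test.

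**The case against.** The strongest reply is that this is a wording slip. The operative treatment procedure is section a. Recording side-effects every 12 weeks for two years makes little sense if the first one ended participation, and the attrition allowance of 20% or less for all causes points the same way. Stopping only for serious or intolerable effects is the likely intent. This is fair and keeps the severity low. It does not remove the contradiction, because item 5 is the stated risk-minimisation rule and nothing in the document narrows it.

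A second reply is that a cautious stopping rule is legitimate in a cognitively impaired population, and that treatment here is naturalistic and given in ordinary care. That also stands. Any amendment should define when protocol participation ends and should not limit a clinician's freedom to stop a drug.

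A reader might go further and infer that item 5 biases Hypothesis 2 in favour of the combination. The documents do not support this. Hypothesis 2 is a contrast between groups, and neither the side-effect stopping rule applied to Group 2 nor its scan intervals are given. Group 1 intervals are not given either, and the earlier untreated cohort's ranged from 1.0 to 2.6 years. A reader might also take item 4's figure of about 10% for donepezil side-effects as an exit rate. It is a side-effect frequency, and none is given for memantine.

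**Conclusion.** The contradiction between item 5 and section a holds for both drugs, and the tension with item 4 holds for donepezil. Applied literally, item 5 would needlessly remove Group 3 subjects with minor side-effects and, if it ends participation, advance their second MRI.

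The size is not determinable, because exit shares, exit times and memantine side-effect frequency are not given. The worked figures rest on assumptions: linear loss at the untreated rate, exit at 0.25 to 1 year, 2% or 10% leaving early, and five further removals. They indicate a modest effect. A distortion of the Group 3 versus Group 2 comparison is not established.

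The lack of any interval adjustment is a separate weakness that does not depend on how item 5 is read. The team's earlier longitudinal study covaried for scan interval (group effect p = 0.015), and section h does not say that this one will. Low severity, worth correcting because both changes are cheap.

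**What to change.** 1. Amend item 5 along these lines: *Protocol participation will be discontinued for serious or intolerable side-effects. Other side-effects will be managed clinically (for donepezil, by reduction to 5 mg/day), and subjects on a reduced dose will remain on the scheduled assessments and the two-year MRI. Nothing here restricts the treating clinician's freedom to stop a drug.*

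2. Separately, in section h, analyse volume and thickness change per year (difference divided by scan interval) or adjust for scan interval. State whether scans taken at early exit enter the Hypothesis 2 analysis.

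The cost is a short wording change in item 5 and a short addition to the analysis section, with no added visits for dose-reduced subjects. There are two drawbacks. Some subjects will be followed on a reduced dose. Annualised changes from short intervals are also noisier: the same measurement error divided by 0.5 year instead of 2 years counts 2/0.5 = 4 times as much. This is a reason to settle in advance how early-exit scans are used.
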